11.5 Prior Anti-Cancer Therapy

The prior anti-cancer therapies are collected under the “Prior Anti-Cancer Drug Therapies Details”, “Prior Anti-Cancer Radiotherapy Details”, “Prior Anti-Cancer Surgeries Details”, “Previous EGFR Therapy” and “Previous EGFR Therapy Drugs” eCRF pages.

The number and percentage of participants in each of the following anti-cancer therapy categories will be tabulated:

- Prior anti-cancer drug therapy for locally advanced or metastatic disease (anti-EGFR as prior drug therapy)
 - Number of prior anti-cancer drug therapy lines: 1 / 2 / 3 / 4 / ≥ 5
 - Prior anti-cancer drug therapies
 - Prior anti-cancer drug combinations
 - Best response across all prior anti-cancer drug therapies: Complete Response (CR) / Partial Response (PR) / Stable Disease (SD) / Progressive Disease (PD) / Non-Complete Response/Non-Progressive Disease (Non-CR/Non-PD) / Not Evaluable / Unknown
- Prior anti-cancer radiotherapy
 - Any prior anti-cancer radiotherapy: Yes / No
 - Number of prior anti-cancer radiotherapy regimen: 1 / 2 / 3 / ≥ 4
 - Best response across all prior anti-cancer radiotherapies: Complete Response (CR) / Partial Response (PR) / Stable Disease (SD) / Progressive Disease (PD) / Non-Complete Response/Non-Progressive Disease (Non-CR/Non-PD) / Not Evaluable / Unknown.

- Prior anti-cancer surgery
 - Any prior anti-cancer surgery: Yes / No
 - Number of prior anti-cancer surgeries: 1 / 2 / 3 / ≥ 4
 - Prior anti-cancer surgeries outcome
 - Any prior surgery curative in intent: Yes / No
 - Best outcome across all prior anti-cancer surgeries: No residual tumor after resection (R0) / Tumor/metastases not resected completely with microscopic residual lesions (R1) / Tumor/metastases not resected completely with macroscopic residual lesions (R2) / Metastases not resected (NR), Other

The listings of prior anti-cancer treatments and procedures will also be provided as follows. These will include the participant identification number, and all the relevant collected data fields on the corresponding eCRF pages.

- Listing of prior anti-cancer drug therapies
- Listing of prior anti-cancer radiotherapy
- Listing of prior anti-cancer surgeries

11.6 Other Baseline Characteristics

Information on other characteristics collected at baseline will be summarized and listed. Summary statistics will be presented for

- ECOG PS
- Height, weight, body surface area (BSA), and body mass index (BMI)

Specifications for computation:

- BSA [m²] = $\sqrt{\frac{\text{height}[\text{cm}] \times \text{weight}[\text{kg}]}{3600}}$
- BMI [kg/m²] = $\frac{\text{weight}[\text{kg}]}{\text{height}[\text{cm}]^2} \times 10000$
- In the formula above, values at baseline should be used for both weight and height.

ECOG PS, height, weight, BSA and BMI will be added to the listing presenting demographic data.

Other baseline characteristics such as vital signs, clinical laboratory evaluations and ECGs will be part of Section 15 (Safety Analyses).

12

Previous or Concomitant Medications/Procedures

The following analyses will be performed based on the SAF analysis set and presented as indicated in Section 9.

Concomitant medications are medications, other than study treatment, which are taken by participants any time during the on-treatment period, see Section 9.7.

Previous medications are medications, other than study treatment and pre-medications for study treatments, which started before first administration of study treatments.

A medication may be classified as both concomitant and previous. The respective flags will be derived based on start and end date. To derive these flags in case of missing or partial dates, see Section 9.8.

Concomitant and previous medications each will be summarized by number and percentage of participants from the “Concomitant Medications Details” eCRF page. ATC-2nd level and preferred term level will be tabulated as given from the WHO-DD dictionary most current version. If any previous or concomitant medication is classified into multiple ATC classes, the medication will be summarized separately under each of these ATC classes. The summary tables will be sorted by ATC-2nd level and preferred term in alphabetical order. In case any specific medication does not have an ATC-2nd level coded term, it will be summarized under “UNCODED” ATC classification category. Each participant will only be counted once, even if he/she received the same medication at different times.

Any medication recorded on the “Concomitant Medications Details” eCRF page will be listed with an indication of whether the medication was previous, concomitant or both.

All **concurrent procedures**, which were undertaken during the on-treatment period, will be summarized according to the “Concomitant Procedures Details” eCRF page. Concurrent procedures will be classified using the most recent MedDRA version at the time of analysis.

A procedure will be considered concurrent if it started before the first dose of study treatment and was still ongoing when study treatment started or if it started after the first dose but during the on-treatment period. Number and percentage of participants with concurrent procedures will be presented by SOC and PT in descending frequency of the total column.

A listing with the relevant information about concurrent procedures will also be produced. A flag will be added to indicate whether the procedure is:

- Prior: the procedure started before the first dose of study treatment
- Concurrent: as defined above
- Post: the procedure started after the on-treatment period or during the on-treatment period but was still ongoing at the end of it.

A procedure could therefore be prior and concurrent as well as concurrent and post-treatment.

Subsequent anti-cancer therapy

The subsequent anti-cancer therapies are collected under the “Anti-Cancer Treatment After Discontinuation Details”, “Radiotherapy after Discontinuation Details” and “Anti-Cancer Treatment After Discontinuation Details – Maximum Drugs” eCRF pages.

The number and percentage of participants in each of the following anti-cancer treatment categories will be tabulated:

- Number of participants with subsequent anti-cancer treatment
- Subsequent anti-cancer drug therapy
 - Any subsequent anti-cancer drug therapy: Yes / No
 - Number of subsequent anti-cancer drug therapy lines: 1 / 2 / 3 / ≥ 4
 - Type of therapy
 - Intent of therapy: Metastatic/Locally advanced / Neoadjuvant / Adjuvant
 - Subsequent anti-cancer drugs
 - Best response across all subsequent anti-cancer drug therapies: Complete Response (CR) / Partial Response (PR) / Stable Disease (SD) / Progressive Disease (PD) / Non-Complete Response/Non-Progressive Disease (Non-CR/Non-PD) / Not Evaluable / Unknown. For participants who received more than one anti-cancer drug therapy after treatment discontinuation, the best overall response among all anti-cancer drug therapies will be summarized.
- Subsequent radiotherapy
 - Any subsequent anti-cancer radiotherapy: Yes / No

The listings of subsequent anti-cancer treatments will also be provided as follows. These will include the participant identification number, and all the relevant collected data-fields on the corresponding eCRF pages.

- Listing of subsequent anti-cancer drug therapies
- Listing of subsequent anti-cancer radiotherapy

13 Study Treatment: Compliance and Exposure

All summaries and listings related to study treatment compliance and exposure will be based on the SAF analysis set.

All dosing calculations and summaries will be based on “Tepotinib Administration” and “Cetuximab Administration” CRF pages. The date of last drug administration will be taken from the “Tepotinib Termination” and “Cetuximab Termination” eCRF pages for those participants who have discontinued treatment by the cut-off date whereas for those participants who are still on-treatment, the last dosing date before or at the cut-off date will be used.

The date of last study drug administration will be defined as the last date in the “Tepotinib Administration” and “Cetuximab Administration” CRF pages, with dose > 0.

A dose of tepotinib will be regarded as being taken on a particular day if the actual dose of tepotinib taken is > 0 mg. Therefore, interruptions, compliance, and dose changes are not taken into account for the calculation of duration of therapy. The same would apply to cetuximab.

The following summary tables will be provided:

- Duration of therapy (weeks)
- Total number of 3-week cycles
- Cumulative actual dose (mg)
- Dose intensity (mg/3-week cycle)
- Relative dose intensity (%)
- Number of cetuximab infusions

Duration of therapy

Duration of therapy is defined as

$$\text{Duration of therapy (in weeks)} = \left(\frac{\text{Date of last dosing day} - \text{Date of first dosing day} + D}{7} \right)$$

where D = 1 for tepotinib and D = 7 for cetuximab.

The total number of 3-week cycles is defined as the duration of therapy (in weeks)/3.

For categorical summary, use floor (duration of therapy) i.e. round the value to completed cycles. For summary statistics take the duration value as such.

Cumulative actual dose of tepotinib

The cumulative actual dose (mg) per participant in a time period is the sum of the total doses that the participant received within that period (i.e. total dose administered (mg)).

Dose intensity and relative dose intensity of tepotinib

The dose intensity and the relative dose intensity will be calculated for a 3-week cycle. The dose intensity (mg/3-week cycle) per participant is defined as:

$$\text{Actual dose intensity (mg/3-week cycle)} = \left(\frac{\text{Cumulative actual dose (mg)}}{\text{Total number of 3-week cycles}} \right)$$

Relative dose intensity per participant is defined as:

$$\text{Relative dose intensity (\%)} = 100 \times \left(\frac{\text{Actual dose intensity}}{\text{Intended dose intensity by 3-week cycle}} \right)$$

where intended dose intensity (mg/3-week cycle) = RP2D mg * 21 days for tepotinib.

A dose of cetuximab is regarded to be administered, if the actual dose of cetuximab received is > 0, or the duration of the infusion is > 0.

For Cycle X, actual cycle start date for each participant is

- the earliest start date of dosing in the Cycle X day 1 visit eCRF exposure page, if the participant received study treatment on that visit (i.e., any study drug with dose > 0 at that visit)
- the first day of assessments in the Cycle X day 1 visit, if the participant did not receive study treatment on that visit (i.e., all study drugs had dose = 0 at that visit). Use start date in the exposure page if available; if start date is not available then use date of collection of vital signs (assuming vital signs are the first assessment of the cycle on Cycle X day 1 visit).

Actual cycle end date for each participant is,

- for all cycles X except the last cycle, actual cycle end date = actual cycle (X+1) start date – 1 day;
- for the last cycle, actual cycle end date = actual cycle start date + intended cycle duration (21 days) – 1 day

Cumulative actual dose of cetuximab

The cumulative dose (mg/m²) from 1st infusion per participant in a time period is the sum of the total dose levels that the participant received within that period (i.e. total dose administered (mg) / recalculated BSA (m²)).

Dose intensity and relative dose intensity of cetuximab

Actual dose intensity (mg/m²/3-week cycle) per participant is defined as:

$$\text{Actual dose intensity} = \left(\frac{\text{Cumulative dose from 1st infusion}}{\text{Total number of 3-week cycles}} \right)$$

Relative dose intensity per participant is defined as:

$$\text{Relative dose intensity (\%)} = 100 \times \left(\frac{\text{Actual dose intensity}}{\text{Intended dose intensity by 3-week cycle}} \right)$$

where intended dose intensity by 3-week cycle (mg/m²/3-week cycle) per participant is defined as

- for the first cycle:
 - $400 \text{ mg/m}^2 + 2 \times 250 \text{ mg/m}^2$ per 3-week cycle, if loading dose is needed
 - $3 \times 250 \text{ mg/m}^2$ per 3-week cycle, if loading dose is not needed
- for the subsequent cycles: $3 \times 250 \text{ mg/m}^2$ per 3-week cycle

Dose reductions

If the 500 mg dose for tepotinib will be the selected RP2D, participants may have a dose reduction to 250 mg, which is also the minimum possible dose in this study. If 250 mg is the RP2D for tepotinib, then no further reduction will be possible.

For cetuximab the loading dose is 400 mg/m² and subsequent weekly doses are 250 mg/m² if the loading dose is required or the weekly dose is 250 mg/m² if the loading dose is not required. The weekly dose can be reduced to 200 mg/m² or 150 mg/m² for safety reasons if necessary.

The number of participants with and without any dose reduction will be summarized. In case the selected RP2D is 250 mg, the tepotinib sections will contain “NA” (Not Applicable).

Number of participants with any dose adjustment due to Adverse Event/Other will be provided.

Dose interruptions and therapy delays

For tepotinib any days within the treatment period where the participants did not take any tepotinib will be counted as dose interruptions. Number of participants with any tepotinib interruptions will be presented.

Dose delays are applicable for cetuximab only. It will be derived by administration as the number of days between two successive administrations greater than 7 and will be presented as follows:

- Number of participants with delayed infusions, and maximum length of delay (no delay, 3-8 days, 9-15 days, ≥ 16 days) – worst case

Treatment administration of tepotinib and cetuximab by time point will be listed.

14 Efficacy Analyses

The following analyses will be performed based on the FAS and will be presented by cohort and assigned dose level of tepotinib, except when otherwise stated.

14.1 Primary Endpoint (Overall Study): Objective Response

14.1.1 Derivation and analysis

Best Overall response (BOR) will be assessed based on reported overall responses at different evaluation time points from the study treatment start date until documented disease progression in accordance to RECIST v1.1 by investigator, taking requirements for confirmation into account as detailed below.

Only tumor assessments performed before the start of any subsequent anti-cancer therapies will be considered in the assessment of BOR. If a tumor assessment was performed on the same day as start of new anti-cancer therapy, it will be assumed that the tumor assessment was performed prior to the start of the new anti-cancer therapy, therefore the tumor assessment will be included in the assessment of BOR.

Clinical deterioration will not be considered as documented disease progression. The date of the overall response assessment is the earliest date for imaging of target, non-target and new lesions of images taken at that response assessment.

BOR Based on Confirmed Responses:

- Complete Response (CR) = at least two determinations of CR at least 4 weeks apart (with no PD in between)
- Partial Response (PR) = at least two determinations of PR or better (PR followed by PR or PR followed by CR) at least 4 weeks apart (and not qualifying for a CR), with no PD in between
- Stable Disease (SD) = at least one SD assessment (or better) \geq 6 weeks after start date (and not qualifying for CR or PR).
- Non-CR/non-PD (applicable only to participants with non-measurable disease at baseline) = at least one non-CR/non-PD assessment (or better) \geq 6 weeks after start date (and not qualifying for CR or PR).
- Progressive Disease (PD) = PD \leq 12 weeks after start date of study treatment (and not qualifying for CR, PR, non-CR/non-PD or SD).
- Not Evaluable (NE): all other cases.

SD can follow PR only in the rare case that tumor increases by less than 20% from the nadir, but enough that a previously documented 30% decrease from baseline no longer holds. If this occurs the sequence PR-SD-PR is considered a confirmed PR. A sequence of PR – SD – SD – PD would be a best response of SD if the minimum duration for SD definition has been met.

Participants are defined as having an Objective Response (OR) if they achieved either a BOR of confirmed CR or confirmed PR according to RECIST v1.1 as assessed by the investigator, from first administration of study treatment to first observation of PD.

Participants who do not have an on-treatment radiographic tumor assessment due to early progression, who receive anti-tumor treatments other than the study treatments prior to reaching confirmed CR or

PR, or who die, progress, or drop out for any reason prior to reaching confirmed CR or PR will be counted as non-responders in the assessment of OR. Each participant will have an objective response status (0: 'no OR'; 1: 'OR'). OR rate (ORR) is the proportion of participants with OR in the analysis set. No formal statistical hypotheses will be tested.

The number and percentage of participants with BOR of confirmed CR, confirmed PR, SD, PD, and NE will be tabulated.

The confirmed ORR by cohort and assigned dose level of tepotinib will be presented along with the two-sided 95% CI using the Clopper-Pearson method (1934) (exact CI for a binomial proportion as computed by default by the SAS FREQ procedure using the EXACT option).

A spider plot will show the participant profiles of the sum of target lesion diameters (sum of longest diameters for non-nodal lesions, short axis for nodal lesions) over time (presenting all participants on the same graph). In addition, a waterfall plot will show the change in sum of target lesion diameters between baseline and the best post-baseline assessment for each participant.

Time to and duration of response by investigator assessment for every participant will be plotted using a swimmer plot. Color coded symbols will be used to show the time of the following events: CR, PR, PD, death, ongoing response and end of treatment.

Estimand Attributes

Endpoint:

- OR according to RECIST 1.1 assessed by Investigator prior to further anti-cancer therapy and progression

Population:

- Participants with *RAS/BRAF* wild-type left-sided metastatic colorectal cancer (mCRC) having acquired resistance to anti-EGFR antibody targeting therapy due to *MET* amplification

Treatment:

- Tepotinib combined with cetuximab

Intercurrent Event Strategy:

- Discontinuation of treatment (treatment-policy strategy, i.e. regardless of the intercurrent event)
- Start of subsequent anti-cancer therapy (while not treated with subsequent anti-cancer therapy strategy, i.e. assessments up_to the intercurrent event)
- Progression according to RECIST 1.1 (while not progressed strategy, i.e. assessments up_to the intercurrent event)

Population Level Summary:

- Rate

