Activity / Assessment	Screening / Baseline	Intervention Period (in cycles of 3 weeks)									EoT	Safety Follow up / Discontinuation	Survival Follow-Up / EoS / 1-Year Follow-Up	Notes
	Day -56 to Day -1	Cycle 1 (21 days)		Cycle 2 (21 days)		Cycle 3 and subsequent cycles (21 days)		Within 14 days after decision to withdraw IMP	30 days after the last dose	After Safety Follow-Up, every 3 months, up to 1-year Site Visit or by Telephone				
Cycle Day		1	8	15	1	8	15	1	8	15				
Visit Window		± 3 days			± 3 days			± 3 days				- 3 to + 7 days	± 1 month	
ctDNA sample	X							Cycle 3, 5, 9 and 13 only			X			Collection predose (within 60 min prior to tepotinib dose), before premedication, if applicable (See Appendix 4)
Documentation of RAS/BRAF wild-type status, and high MET amp levels	X													Confirmed prior to enrollment and after disease progression on the previous anti-EGFR therapy by an established test.
Tepotinib until PD or intolerance		QD												Decided by the Sponsor and SMC: Dosing may be stopped at any time to review safety and PK data and allow for adjustments before dosing is resumed. Additional schedules may also be evaluated.
Cetuximab until PD or intolerance		Weekly (Day 1)												See Section 6.1 for details of premedication required prior to first infusion.

Activity / Assessment	Screening / Baseline	Intervention Period (in cycles of 3 weeks)									EoT	Safety Follow up / Discontinuation	Survival Follow-Up / EoS / 1-Year Follow-Up	Notes
	Day -56 to Day -1	Cycle 1 (21 days)		Cycle 2 (21 days)		Cycle 3 and subsequent cycles (21 days)		Within 14 days after decision to withdraw IMP	30 days after the last dose	After Safety Follow-Up, every 3 months, up to 1-year Site Visit or by Telephone				
Cycle Day		1	8	15	1	8	15	1	8	15				
Visit Window		± 3 days		± 3 days		± 3 days			- 3 to + 7 days		± 1 month			
Tumor Assessment (RECIST Version 1.1) based on MRI and/or CT scans and other protocol-defined imaging modalities.	X							X #)					See Section 8.1 Screening tumor assessment needs to happen within 28 days prior to dosing. All evaluations should be documented by the Investigator and images uploaded to the imaging repository, for a possible independent read at a later date. #): C3, C5, C7, C9, C11, C13, C15 and subsequently every 4 cycles until study closure, or disease progression regardless of study intervention modifications/discontinuation. If disease progression is not certain, consider continuing to image.	

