#### Duration of study for each participant, and duration of the study intervention period

For each participant, the study will include a Screening Period of up to 56 days, a Study

Intervention Period consisting of 3-week cycles (Cycles are 21 days) of tepotinib combined with cetuximab until disease progression, an End-of-Study Intervention Visit, a Safety Follow-up Period of 30 days, and a 1-year post study follow-up. Therefore, assuming there are 5 cycles, the anticipated duration of treatment for each participant is 191 days or ~6.5 months with a 1-year follow-up period thereafter.

Participants who discontinue the study for any reason, except for participant withdrawal, will complete the End-of-Study Intervention (End of Treatment), and Safety Follow-up Visit. See Section 1.3.

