Cytology results will be collected when available. Enlarging pleural/pericardial effusion and/or ascites (fluid collections) may or may not denote progression. The radiologist can utilize cytology findings (if available) to decide if significant new fluid or unequivocal and significant enlarging fluid is an indication of progression.

The Investigator may perform scans in addition to a scheduled study scan for medical reasons or if the Investigator suspects PD. Participants who withdraw from the study for clinical or symptomatic deterioration before objective documentation of PD will be requested to undergo appropriate imaging to confirm PD. Every effort should be made to confirm a clinical diagnosis of PD by imaging according to RECIST Version 1.1.

Participants will be assessed every 6 weeks starting from Cycle 3 Day 1 visit until 9 months, and every 12 weeks thereafter according to RECIST Version 1.1, until disease progression, death, withdrawal of consent, or study closure. Details on how to perform RECIST Version 1.1

assessments are provided in [Appendix 5](#). Investigator assessments will be conducted. Any CR or PR should be confirmed, preferably at the scheduled 6-week interval or at the next scheduled imaging visit, but no sooner than 4 weeks after the initial documentation of CR or PR. In the case of symptoms suggesting progression, participants should be evaluated by imaging thereafter for documentation and confirmation of the tumor responses.

The same method of assessment and the same technique should be used to characterize each identified and reported lesion at Baseline and during the study. If a chest X-ray indicates metastatic disease while the participant is enrolled in this study, a CT of the chest is required for confirmation. All assessments should be provided by the same physician or radiologist if possible during the study.

Participants who withdraw from the treatment for reasons other than progressive disease will have additional visits for tumor assessments every 6 weeks until 9 months, and every 12 weeks thereafter until disease progression. A  $\pm$  7-day time window is permitted for these additional follow-up visits until 9 months, and  $\pm$  14 days thereafter. Reasons for study termination should be recorded if this visit is the last visit for the participant. Recording of any new anticancer therapy will be made (a tumor assessment is mandatory before initiating the new therapy).

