## 9.4 Statistical Analyses

### 9.4.1 Efficacy Analyses

All efficacy analyses will be performed on the FAS population unless otherwise specified. These analyses will be done by cohort and assigned dose level of tepotinib. There is no formal significance level for this study and all analyses are considered descriptive.

Endpoint	Statistical Analysis Methods
Primary	
Objective response determined according to RECIST Version 1.1 by Investigator Assessment	
Best Overall Response (BOR) based on confirmed responses will be derived as follows:
 

• Complete Response (CR) defined as at least two determinations of CR at least 4 weeks apart (with no PD in between)

• Partial Response (PR) defined as at least two determinations of PR or better (PR followed by PR or PR followed by CR) at least 4 weeks apart (and not qualifying for a CR), with no PD in between

• Stable Disease (SD) defined as at least one SD assessment (or better) [<math>\geq 6</math> weeks] after start date (and not qualifying for confirmed CR or PR).

• Non-CR/non-PD (applicable only to participants with non-measurable disease at Baseline) = at least one non-CR/non-PD assessment (or better) [<math>\geq 6</math> weeks] after start date (and not qualifying for CR or PR).

• PD = PD <math>\leq 12</math> weeks after start date (and not qualifying for CR, PR, non-CR/non-PD or SD).

• Not Evaluable (NE): all other cases.

 
SD can follow PR only in the rare case that tumor increases by less than 20% from the nadir, but enough that a previously documented 30% decrease from Baseline no longer holds. If this occurs the sequence PR-SD-PR is considered a confirmed PR. A sequence of PR – SD – SD – PD would be a best response of SD if the minimum duration for SD definition has been met.
 
Objective Response (OR) is defined as a BOR of complete response (CR) or partial response (PR) according to RECIST Version 1.1.
 
Objective response rate (confirmed CR or PR) and the corresponding 2-sided exact Clopper-Pearson 95% CI will be presented.

Secondary	

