6.2 Interim analysis for futility

A futility analysis will be performed after the first 12 participants are enrolled for second line (2L) treatment (Cohort A). The date 13 weeks after the first dose date (the scheduled time point of the second scan, C5D1, including a time window of 7 days) of the 12th patient enrolled will be used here as cut-off date. Recruitment of further participants into this study, both cohorts, will continue. If there are less than 2 responders (confirmed CR or PR) within the first 12 participants treated with RP2D, the enrolment of 2L participants for this study might be stopped for futility.

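### The SD and PD time limits for best overall response sit on the nominal scan days with no window, so documented progression just after week 12 can be tabulated as not evaluable

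*SAP*

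**What the plan says.** SAP 14.1.1 and Protocol 9.4.1 derive BOR by the same rules.

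- SD needs at least one assessment of SD or better no earlier than "6 weeks after start date (and not qualifying for CR or PR".
- PD counts only if it occurs no later than "12 weeks after start date of study treatment (and not qualifying for CR, PR, non-CR/non-PD or SD".
- The residual category is "Not Evaluable (NE): all other cases".

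Neither text gives a visit-window allowance for the 6 or the 12 weeks.

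The scan schedule comes from three places. Protocol 4.1 describes "3-week cycles (Cycles are 21 days" each. The Schedule of Activities (Protocol 1.3) puts scans at "C3, C5, C7, C9, C11, C13, C15 and subsequently every 4 cycles until study closure", with a visit window of ±3 days for Cycle 3 and later. Protocol 8.1.1 agrees: "Participants will be assessed every 6 weeks starting from Cycle 3 Day 1 visit until 9 months".

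A wider window appears elsewhere. SAP 6.2 sets the futility cut-off at 13 weeks, which it explains as "the scheduled time point of the second scan, C5D1, including a time window of 7 days". For scans after stopping treatment, Protocol 8.1.1 says that a ± "7-day time window is permitted for these additional follow-up visits until 9 months".

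Protocol Appendix 5 (Evaluation of Best Overall Response) takes the example of SD at the first assessment and PD at the second, with the SD minimum not met. The best response is PD, and no upper time limit is attached. The same participant is inevaluable only if lost to follow-up after the first scan.

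**The concern.** A time limit placed exactly on a nominal visit day splits compliant visits into two groups by a day or two of scheduling. Here that happens at both limits. A first scan slightly early fails the SD minimum, and a second scan slightly late falls outside the PD limit. A participant with both has radiologically documented progression but drops into the residual NE category. So does a participant whose first scan is not evaluable and whose second scan shows PD after day 84.

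NE normally tells a reader that data were missing or unusable. The BOR table is reported with the primary endpoint (SAP 14.1.1), by subgroup (SAP 14.1.4) and at the futility look (SAP 14.1.3). With 22 and 20 participants planned, one relabelled participant moves a category by 1/22 = 4.5 or 1/20 = 5.0 percentage points.

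**Working it through.** Days below are elapsed days, that is, assessment date minus start date, unless marked +1.

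**1. The plan's own figure.** C5D1 is 4 × 21 = 84 days after C1D1. Adding the 7 days of SAP 6.2 gives 91 days = 13 weeks, which reproduces the stated futility cut-off.

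**2. Where the limits fall.** C3D1 is 2 × 21 = 42 days = 6.0 weeks, which is the SD limit. C5D1 is 84 days = 12.0 weeks, which is the PD limit.

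**3. One disease course, three labels.** Take SD at scan 1 and PD at scan 2, with every scan within ±3 days of nominal:

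| Scan 1 | Scan 2 | BOR under the plan |
|---|---|---|
| day 42 | day 84 | SD |
| day 40 | day 84 | PD |
| day 40 | day 86 | NE |

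For the second and third rows, Appendix 5 gives PD. Only the third row disagrees with it.

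**4. How many in-window pairs give NE.** For this course, NE needs scan 1 before day 42 and scan 2 after day 84. Within ±3 days that is 3 of 7 days (39–41) and 3 of 7 days (85–87). The count is 3 × 3 = 9 of 49 pairs (18.4%). PD takes 3 × 4 = 12 pairs (24.5%) and SD 4 × 7 = 28 pairs (57.1%).

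**5. Day count.** SAP 9.4 adds one day to durations unless otherwise specified, but not to its time-since variables. It does not say which convention governs these limits. With +1, scan 1 fails SD only on days 39–40 (2 of 7) and scan 2 misses the PD limit on days 84–87 (4 of 7):

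| Window and count | SD | PD | NE |
|---|---|---|---|
| ±3, simple difference | 28/49 | 12/49 | 9/49 (18.4%) |
| ±3, +1 | 35/49 | 6/49 | 8/49 (16.3%) |
| ±7, simple difference | 120/225 | 56/225 | 49/225 (21.8%) |
| ±7, +1 | 135/225 | 42/225 | 48/225 (21.3%) |

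The convention alone moves days 41 and 85 from NE to SD, and days 40 and 84 from PD to NE. Two programmers following the SAP could therefore produce different tables.

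**6. Non-evaluable first scan.** If scan 1 is not evaluable and scan 2 shows PD, BOR is NE on 3 of the 7 in-window days (4 of 7 with +1).

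**7. Check of a window allowance.** Set the SD limit at 42 minus the window and the PD limit at 84 plus the window, with simple differences. With 39 and 87 days, all 49 pairs within ±3 give SD. With 35 and 91 days, all 225 pairs within ±7 give SD. PD first documented at an in-window second scan is then never NE. Using 39 and 87 when the working window is ±7 is not enough: scan 1 on days 35–38 still fails SD, which is 4 × 15 = 60 of 225 pairs.

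**The case against.** The strongest reply is that nothing decided in this trial depends on the split. SD, PD and NE are all non-responses under SAP 14.1.1, the study is descriptive, and tumor data are listed. For SD on day 40 and PD on day 86, the progression is still a PFS event, because 86 − 40 = 46 days is within 84. All of that stands. The PFS reassurance does not extend to the non-evaluable first scan: SAP 14.2.2 (Table 4) then counts from start of treatment, and a PD on day 86 is beyond 84 days. That is a separate rule.

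A second reply is that Appendix 5 leaves the definition of inevaluability to each protocol, that its SD-then-PD example sits in a paragraph on studies without response confirmation, and that its general SD minimum is not less than 6 to 8 weeks. So a 6-week minimum is legitimate, and a protocol may define NE in its own way. But the example turns on SD and PD only, not on confirmation. The protocol as it stands gives two answers for the same participant, and neither document explains why progression seen at a compliant scan should be called not evaluable. Appendix 5 does not address a non-evaluable first scan followed by PD; there the objection is to the label, not a contradiction.

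A reader might infer that 21 of 49 pairs (43%) are misclassified because they lose the SD label. The documents do not support that. Twelve of those 21 become PD, which is what Appendix 5 prescribes when the SD minimum is missed.

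**Conclusion.** The point holds as a minor defect in the BOR derivation. In both documents the SD and PD limits coincide with the nominal first and second scan days, without a window. As a result, documented PD just after day 84, following an early SD or a non-evaluable first scan, is tabulated as NE. For SD followed by PD, this conflicts with Appendix 5.

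The effect is confined to the SD/PD/NE split of the BOR table in the overall, subgroup and futility reports. It would be wrong to read it as a problem with the primary endpoint: ORR, its Clopper-Pearson interval, the futility count and DoR are unchanged.

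The size in participants is unknown. The documents give neither the distribution of scan days nor the proportion with the vulnerable course. The 9/49 (or 8/49) describes that one course with independent, equally likely scan days within ±3, which is an assumption. It is not a forecast for a cohort. Progression at an in-window first scan is always PD, and a scan showing SD or better at or after the 6-week limit and before progression secures the SD label.

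**What to change.** Amend Protocol 9.4.1 and SAP 14.1.1 together:

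1. **PD.** Align with Appendix 5. BOR is PD, not NE, if PD is documented at or before the second scheduled scan including its window, or directly after an SD that misses the minimum.
2. **SD.** State the minimum as 6 weeks minus the permitted scan window, and describe it as a visit-window allowance, because Appendix 5 gives 6 to 8 weeks as the general minimum.
3. **Window.** Use one scan window for both limits, after reconciling the ±3 days of the Schedule of Activities with the 7 days in SAP 6.2. The limits are then 39 and 87 days (±3) or 35 and 91 days (±7).
4. **Day count.** State that days are assessment date minus start date, without the +1 of SAP 9.4.

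The cost is a small edit to the derivation and its programming; no new data are needed. The downside is that the SD threshold becomes a few days shorter than 6 weeks, which should be stated beside the BOR table.
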